c) The research could not practicably be carried out without the requested waiver or alteration.

The investigators require the use of the electronic medical record in the pre-screening period to identify patients on the basis of the current admission and diagnosis and therapy received. For this, we will need access to the patient chart to guarantee study eligibility. Without this access, the study could not be completed. The filter within the electronic medical record will only pull patients who meet inclusion criteria. The chart will then be utilized to verify this information and exclude patients who meet the exclusion criteria.

d) Whenever possible, the subjects or legally authorized representatives will be provided with additional pertinent information after they have participated in the study.

After identifying that a patient is eligible for the study, they or their LAR will be approached with the attached informed consent and provided with pertinent information for the study. If they decline further participation, the electronic medical record will not be accessed by the investigators following.

e) If the research involves using or accessing identifiable private information or identifiable biospecimens, the research could not practicably be carried out without using such information or biospecimens in an identifiable format.

- Private information/specimens are "identifiable" if the investigator may ascertain the identity of the subject or if identifiers are associated with the information (e.g., medical records). This could be any of the 18 HIPAA identifiers including dates of service.
- If not using identifiable private information or identifiable biospecimens, insert N/A below.

Identifiable patient information (the medical record number) is needed to track the patient throughout the duration of the study - this will allow the investigators to data collect the information provided above as well as the location of the patient for blood draws. The patient identifiable information will be kept separate from both the biospecimens and the data collection form on RedCap. Instead, a master list, tying the identifiable patient information to a designated subject, onidentifiable code will be kept by the PI only on the PI's laptop. The non-identifiable assigned code will be placed on the biospecimens and into RedCap to tie subject data to their biospecimen.

Request for Waiver of Documentation of Informed Consent Process

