The primary objective of this study is to evaluate the efficacy of nebulized heparin administration in COVID-19. Our primary outcome will be defined as the mean PaO₂/FiO₂ ratio in the first 10 days of ICU stay. This is the gold standard for hypoxia monitoring in ARDS. Our secondary safety outcome will include clinically significant bleeding, defined as transfusion of red blood cells, required intervention for new-onset bleeding, or death attributed to bleeding during the study period. Additional outcomes will include incidence of VTE, time on mechanical ventilation, ICU duration, and overall mortality.

Study Design: Describe the study design (e.g., single/double blind, parallel, crossover, etc.). Indicate whether or not the subjects will receive placebo medication at some point in the research procedures. Also, indicate whether or not the subjects will be randomized in this study. You may reference sponsor's protocol pages and attach as an appendix in the E-IRB "Additional Information" section, however, a summary paragraph must be provided in the text box below. (Including the study design table from a sponsor's protocol is helpful to IRB members.)

Community-Based Participatory Research: If you are conducting community-based participatory research (CBPR), describe strategies for involvement of community members in the design and implementation of the study, and dissemination of results from the study.

Research Repositories: If the purpose of this submission is to establish a Research Repository (bank, registry) indicate whether the material you plan to collect would or would not be available from a commercial supplier, clinical lab, or established IRB approved research repository. Provide scientific justification for establishment of an additional repository collecting duplicate material. Describe the repository design and operating procedures. For relevant information to include, see the UK Research Biospecimen Bank Guidance [PDF] or the UK Research Registry Guidance [PDF]

We propose a randomized, controlled pilot study of patients admitted with confirmed COVID-19 receiving mechanical ventilation for ARDS (paO₂/FiO₂ ratio =300) within 48 hours. Enrollment will occur by the ICU research team who perform daily review for study enrollment. Patients will be randomized to nebulized heparin (25,000 units in 3 mL sodium chloride [NaCl] every 6 hours) versus

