placebo (5 mL nebulized NaCl every 6 hours) for 10 days or until successful ventilator wean. Drugs will be dispensed by investigational drug services. Patients will be excluded for a history of heparin allergy, terminal status as determined by attending physician, history of thrombosis (prior VTE or cardiovascular event), high risk of bleeding (platelet count < 50,000/ μ L or international normalized ratio > 1.5), or active bleeding. Monitoring will include daily ventilator parameters, complete metabolic panels, and complete blood counts, as well as hourly vital signs as part of standard care. The MICU also has an actively enrolling biobank with respiratory samples which we will use to assess viral load. Additional samples will be collected for coagulation (protein S, thrombin, and histone) monitoring, at baseline, 72 hours, and day 10. Laboratory results, medication administration, and vital sign data will be collected up until 10 days of ICU admission or discharge. Mortality, length of stay, and mechanical ventilation duration will be collected for the entire hospital stay. Based on expected baseline $\text{paO}_2/\text{FiO}_2$ ratio of 118 mmHg, we calculate that we need a sample size of 46 patients (n=23 per group) to detect a 15% improvement in $\text{paO}_2/\text{FiO}_2$ ratio, assuming an alpha of 0.05 and power of 80%. (22)

Attachments

[Back to Top](#)

Study Population: Describe the characteristics of the subject population, such as anticipated number, age range, gender, ethnic background and health status. Identify the criteria for inclusion and exclusion. Explain the rationale for the use of special classes such as fetuses, pregnant women, children, institutionalized, adults with impaired consent capacity, prisoners, economically or educationally disadvantaged persons or others who are likely to be vulnerable.

If women or minorities are included, please address how the inclusion of women and members of minority groups and their subpopulations will help you meet your scientific objectives. Exclusion of women or minorities requires clear and compelling rationale that shows inclusion is inappropriate with respect to the health of the subjects or that inclusion is inappropriate for the purpose of the study. Cost is not an acceptable reason for exclusion except when the study would duplicate data from other sources. Women of childbearing potential should not be excluded routinely from participation in clinical research.

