Subject Recruitment Methods & Privacy: Using active voice, describe plans for the identification and recruitment of subjects, including how the population will be identified, and how initial contact will be made with potential subjects by those having legitimate access to the subjects' identity and the subjects' information.

Describe the setting in which an individual will be interacting with an investigator or how and where members of the research team will

meet potential participants. If applicable, describe proposed outreach programs for recruiting women, minorities, or disparate populations as participants in clinical research. Describe steps taken to minimize undue influence in recruiting potential participants.

Please note: Based upon both legal and ethical concerns, the UK IRB does not approve finder's fees or "cold call" procedures made by research staff unknown to the potential participant. The ORI/IRB does not control permission to any UK listserv, mass mailing list, etc. Investigators must secure prior approval for access and use from owners/managers.

For additional details, see topic "Recruitment of Subjects/Advertising" on ORI's [IRB Survival Handbook web page](#) and the PI Guide to Identification and Recruitment of Human Subjects for Research [\[PDF\]](#).

Potential subjects will be screened based on a screening filter that the study team has previously used in the electronic medical record to screen for studies of acute respiratory failure. Once identified, a study team member will approach the patient's care team to inquire about the study. If allowed, the team member will assess the patient for ability to provide consent as described. If the patient is not eligible to provide informed consent, the legally authorized representative will be approached for written or electronic consent.

[Back to Top](#)

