Patients will be screened for eligibility by a member of the research team. If a patient meets eligibility, then a team member will approach the LAR for informed consent. After enrollment, the patient will be randomized via an online randomization generator to either nebulized heparin (25,000 units in 3 mL sodium chloride [NaCl] every 6 hours) or placebo (5 mL nebulized NaCl every 6 hours) for 10 days or until successful ventilator wean. The nurse will be approached for a 10 mL blood draw to be performed at baseline, 72 hours, and day 10 to assess protein S, thrombin, and histone in the [name] laboratory (BBSRB B306-15 and B306-16). The study team will collect the blood samples. Up to 10 mL of blood will be drawn each time for a maximum of 30 mL total, collected in citrate-containing tubes. Deidentified data will be collected via RedCap from the standard of care charting. Upon study completion, deidentified data will be sent to the statistician for analysis.

Attachments

Data Collection: List the data or attach a list of the data to be collected about or from each subject (e.g. interview script, survey tool, data collection form for existing data).

If the research includes survey or interview procedures, the questionnaire, interview questions or assessment scales should be included in the application (use attachment button below).

The data collection instrument(s) can be submitted with your application in draft form with the understanding that the final copy will be submitted to the IRB for approval prior to use (submit final version to the IRB for review as a modification request if initial IRB approval

was issued while the data collection instrument was in draft form).

Note: The IRB approval process does not include a statistical review. Investigators are strongly encouraged to develop data management and analysis plans in consult with a statistician.

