[Back to Top](#)

Research Materials, Records and Privacy: Identify the sources of research material obtained from living human subjects. Indicate what information (specimens, records, data, genetic information, etc.) will be recorded and whether use will be made of existing specimens, records or data. Explain why this information is needed to conduct the study.

Return of Research Results or Incidental Findings (if applicable):

If research has the potential to identify individual results or discover incidental findings that could affect the health of a subject, describe plans to assess, manage, and if applicable disclose findings with individual subjects or provide justification for not disclosing. For IRB expectations, refer to the UK IRB "Frequently Asked Questions (FAQs) on the Return of Research Results or Incidental Research Findings" [\[PDF\]](#).

Blood specimens will be obtained and processed as described above. This information will be used for research purposes only. The collection of these samples will be documented in the patients' medical records. Patients will be assigned a unique patient number that can only be linked to PHI by study personnel. This master list will be stored on the PI's password-encrypted laptop, located within a locked office. No physical documents will be utilized for this study. We maintain the right to keep, preserve, use, and dispose of the findings of this protocol in accordance with institutional guidelines. The appropriate offices of the federal government (e.g. OHRP) maintain the right to inspect the records of the study at any time. Investigational records from this study will be maintained in a confidential manner; subject names will not be associated with any published results. In the circumstance that a subject regains capacity to provide informed consent after samples have been collected and the subject declines participation in the study, samples will be discarded according to the UK Biological Safety Manual section 10.0 and UK Environmental Management will be contacted.

Confidentiality: Specify where the data and/or specimens will be stored and how the researcher will ensure the privacy and confidentiality of both. Please address the following items or indicate if the following has been addressed in a HIPAA or Limited Review form:

- physical security measures (e.g., locked facility, limited access);
- data security (e.g., password-protection, data encryption);

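### All collected samples are discarded when an enrolled patient regains capacity and declines, so coagulation data can be lost selectively from patients who improve

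*Protocol*

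**What the plan says.** **Who consents.** Under Subject Recruitment Methods & Privacy: "If the patient is not eligible to provide informed consent, the legally authorized representative will be approached for written or electronic consent". Research Procedures describes approaching the representative, and places randomisation after enrolment.

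**What is drawn.** Under Study Design: "Additional samples will be collected for coagulation (protein S, thrombin, and histone) monitoring, at baseline, 72 hours, and day 10". Research Procedures puts this at up to 10 mL per draw and 30 mL in total.

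**What happens on later refusal.** Under Research Materials, Records and Privacy, if a subject "regains capacity to provide informed consent after samples have been collected and the subject declines participation in the study, samples will be discarded". The rule has no conditions, and no alternative is offered to the patient. It does not mention assay results already obtained, chart data already recorded, or further chart follow-up.

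**Where the clinical outcomes come from.** The primary outcome is the mean PaO2/FiO2 "ratio in the first 10 days of ICU stay" (Objectives). Under Research Procedures: "Deidentified data will be collected via RedCap from the standard of care charting". Under Study Design: "Mortality, length of stay, and mechanical ventilation duration will be collected for the entire hospital stay".

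**A second sentence on declining.** In the consent-waiver request, Section 2(d): "If they decline further participation, the electronic medical record will not be accessed by the investigators following". It comes directly after "After identifying that a patient is eligible for the study, they or their LAR will be approached with the attached informed consent".

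**The concern.** The discard rule is triggered by something that happens after randomisation and is tied to the course of the illness. A patient has to come round far enough to regain capacity before being able to decline. A patient who dies or stays sedated cannot. The samples removed are therefore not a random subset: they come from the better end of each arm.

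The Background rests the case for the treatment on coagulopathy, and these three markers are the trial's direct evidence on that mechanism. Because the baseline tube is discarded with the others, a refusing patient contributes neither a level nor a change from baseline. Choices about missing data can be left to an analysis plan. Destroyed samples cannot, because no later analysis brings them back.

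**Working it through.** The protocol states no refusal rate, recovery rate or marker distribution, so there is no figure to reproduce. The check has two parts.

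**1. Which data the rule reaches**

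| Data | Source | Removed by the discard rule? |
|---|---|---|
| Protein S, thrombin, histone (baseline, 72 h, day 10) | study blood samples | Yes, unless assayed earlier and the result kept, which is not stated |
| PaO2/FiO2 over the first 10 ICU days | chart | No |
| Mortality, ventilation time, length of stay | chart | No |

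Each refusal removes up to 3 samples. Two refusals in one arm remove 2/23 = 8.7% of its patients from the marker data, and three remove 3/23 = 13.0%.

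**2. How far a marker comparison could move (all inputs assumed)**

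Let *r* be the proportion of an arm that recovers capacity, *q* the proportion of those who then decline, and *D* the difference in mean marker level between recoverers and the rest. Suppose every patient would otherwise have a sample, and that decliners resemble other recoverers. After discarding, the proportion of recoverers left among the samples is

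f(r, q) = r(1 − q) / [r(1 − q) + 1 − r],

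and the observed difference between arms is D × [f(heparin) − f(control)]. Take r = 0.5 on heparin and 0.4 on control, so the full difference is 0.100 D.

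- Equal refusal, q = 0.20 in both arms: f = 0.40/0.90 = 0.4444 and 0.32/0.92 = 0.3478. The difference is 0.0966 D, a shrinkage of 3.4%.
- q = 0.20 on heparin and 0.05 on control: f = 0.4444 and 0.38/0.98 = 0.3878. The difference is 0.0567 D, a shrinkage of 43%.
- q = 0.05 on heparin and 0.20 on control: f = 0.475/0.975 = 0.4872 and 0.3478. The difference is 0.1394 D, an inflation of 39%.
- No effect on recovery (r = 0.4 in both arms), q = 0.05 and 0.20: 0.3878 − 0.3478 gives a spurious difference of 0.040 D. With equal q it is zero.

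Even under equal refusal the mean of each arm moves more than the difference does: −0.056 D on heparin and −0.052 D on control in the first case.

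The unequal cases need very few patients. On heparin, q = 0.20 means 0.20 × 0.5 × 23 = 2.3 refusals. On control, q = 0.05 means 0.05 × 0.4 × 23 = 0.5. Two refusals against none or one can arise by chance.

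**The case against.** **The rule protects the patient.** Someone who never agreed in person and now refuses is entitled to have the samples destroyed. This stands, and the proposal keeps that right. It does not follow that destruction must be the only outcome for a patient who would be content to have the samples used.

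**The markers are not among the outcomes listed under Objectives.** This also stands, and it limits the weight of the point to mechanistic data.

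**The consent form was not available for this review and may already offer choices.** That is possible. The protocol's unconditional rule would then conflict with the form and would need aligning. The same paragraph reserves a right to keep and use findings, which might cover completed assay results, but it does not say so.

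**If refusal is equally likely in both arms, bias is small.** This is correct, as the first case above shows. Equality cannot be assumed, though. Study Design does not state blinding, the nebulised volumes differ (3 mL and 5 mL), and 23 patients per arm leave room for chance imbalance.

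**A stronger reading is tempting.** A reader might infer from Section 2(d) that the chart is also closed for enrolled patients who decline, so that good clinical outcomes disappear. With an assumed 12 deaths, 12/23 = 52% would become 12/20 = 60% once three survivors dropped out. The documents do not support this. Section 2(d) belongs to a request about pre-screening, and its sentence follows the first consent approach, before randomisation. No passage orders deletion of recorded data or an end to follow-up. If the sentence were stretched to enrolled patients, it would also cover refusals by representatives, and the loss would no longer be confined to those who recover.

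**Conclusion.** The point holds for the coagulation samples. An unconditional discard rule acts after randomisation and only on patients who improve enough to decide for themselves. It can therefore remove protein S, thrombin and histone data selectively and beyond recovery. That only improvers can trigger it is an inference from the requirement to regain capacity, but a close one.

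The size is unknown. Bias between arms would be small under equal refusal. Under unequal refusal it could be material in either direction. The percentages above rest wholly on assumed recovery and refusal rates and on the simple mixture described.

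A reader might also infer that the rule erodes the 23 per group or works against the better arm. Neither follows. The sample size is set on PaO2/FiO2, which is not measured from these samples, and the direction of any bias depends on refusal rates the protocol does not give. The 2(d) sentence is loosely worded and worth tightening, but on its natural reading it removes no randomised patient.

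**What to change.** 1. In Research Materials, Records and Privacy, and in the consent form, offer a patient who regains capacity three separate choices: (a) stop study procedures but allow use of samples, results and continued chart follow-up; (b) stop everything but allow use of what has been collected to date; (c) withdraw fully, with samples discarded. Discard samples only under (c) or at the patient's request.
2. State what happens under each choice to assay results already obtained and to data already entered.
3. Record each choice and report the numbers by arm, so that a reader can judge whether the loss was balanced.
4. In the waiver request, Section 2(d), say that the no-access sentence applies to refusal before enrolment. It then cannot be read against the whole-stay collection of mortality, length of stay and ventilation time in Study Design.

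The cost is a few sentences in the protocol and consent form and a slightly longer re-consent conversation. The right to withdraw is unchanged. The change has to be made before samples are destroyed, because the loss cannot be reversed.
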